11.3 Registration Procedures

The items detailed in section 4.2.1 (for phase I patients) and 4.2.2 (for phase II patients) must be submitted in order for the patient to be registered and an identification number assigned.

11.4 Data Submission:

Once a subject is confirmed and registered to the study, eCRFs should be submitted according to the detailed data submission guidelines (provided in a

separate document). Generally, all data for phase I patients during the time period patients are evaluated for Dose Limiting Toxicities (DLTs) must be submitted on a weekly basis. Generally, for all phase II patients, data are due at the end of every cycle.

To develop your data submission guideline, contact [contact].

11.5 Instructions for Participating Sites

Before the study can be initiated at any site, the following documentation must be provided to the Clinical Research Office at Northwestern University:

- Signed and completed Letter of Invitation to participate in the study.
- Signed copy of Northwestern University's Data Monitoring Committee policy pertaining to data submission.
- Draft informed consent form should for review/approval prior to submission to the local IRB
- A copy of the official IRB approval letter for the protocol and informed consent.
- CVs and medical licensure for the local PI and any sub-investigators who will be involved in the study at the site.
- Form FDA 1572 appropriately filled out and signed with appropriate documentation.

Additional activities may be required prior to site activation (i.e. contract execution, study-specific training). Full requirements will be outlined in a memo upon receipt of the signed Letter of Invitation.

11.6 Data Management and Monitoring/Auditing

This study will be conducted in compliance with the Data Safety Monitoring Plan (DSMP) of the Robert H. Lurie Comprehensive Cancer Center of Northwestern University (please refer to Appendices for additional information). The level of risk attributed to this study requires [high level of monitoring](#) as outlined in the DSMP(<http://cancer.northwestern.edu/CRO/data/DataAndSafetyMonitoringPlanMay2014.pdf>). The assigned QAM, with oversight from the Data Monitoring Committee, will monitor this study in accordance with the study phase and risk level. Please refer to the Appendices for additional data submission instructions.

11.7 Adherence to the Protocol

Except for an emergency situation in which proper care for the protection, safety, and well-being of the study patient requires alternative treatment, the study shall be conducted exactly as described in the approved protocol.

11.7.1 Emergency Modifications

Investigators may implement a deviation from, or a change of, the protocol to eliminate an immediate hazard(s) to trial subjects without prior IRB approval.

For any such emergency modification implemented, an IRB modification form must be completed within 5 business days of making the change, and the QAM must be notified within 24 hours of such change.

11.7.2 Other Protocol Deviations

All other deviations from the protocol must be reported to the assigned QAM using the appropriate form.

A protocol deviation is any unplanned variance from an IRB approved protocol that:

- Is generally noted or recognized after it occurs.
- Has no substantive effect on the risks to research participants.
- Has no substantive effect on the scientific integrity of the research plan or the value of the data collected.
- Did not result from willful or knowing misconduct on the part of the investigator(s).

A protocol deviation may be considered an instance of Reportable New Information (RNI) if it:

- Has harmed or increased the risk of harm to one or more research participants.
- Has damaged the scientific integrity of the data collected for the study.
- Results from willful or knowing misconduct on the part of the investigator(s).
- Demonstrates serious or continuing noncompliance with federal regulations, State laws, or University policies.

11.8 Investigator Obligations

The Principal Investigator is responsible for the conduct of the clinical trial at the site in accordance with Title 21 of the Code of Federal Regulations and/or the Declaration of Helsinki. The PI is responsible for personally overseeing the treatment of all study patients. The PI must assure that all study site personnel, including sub-investigators and other study staff members, adhere to the study protocol and all FDA/GCP/NCI regulations and guidelines regarding clinical trials both during and after study completion.

The Principal Investigator at each institution or site will be responsible for assuring that all the required data will be collected, entered onto the appropriate eCRFs, and submitted within the study-specific timeframes. Periodically,

monitoring visits may be conducted and the Principal Investigator will provide access to his/her original records to permit verification of proper entry of data. The study may also be subject to routine audits by the Audit Committee, as outlined in the DSMP.

11.9 Publication Policy

All potential publications and/or data for potential publications (e.g. manuscripts, abstracts, posters, clinicaltrials.gov releases) must be approved in accordance with the policies and processes set forth in the Lurie Cancer Center DSMP. For trials that require high intensity monitoring, the assigned QAM will prepare a preliminary data summary (to be approved by the DMC) no later than 3 months after the study reaches its primary completion date (the date that the final subject is examined or receives an intervention for the purposes of final data collection for the primary endpoint). If the investigator's wish to obtain DMC-approved data prior to this point (or prior to the point dictated by study design), the PI must send a written request for data to the QAM which includes justification. If the request is approved, data will be provided no later than 4 weeks after this request approval. The data will be presented to the DMC at their next available meeting, and a final, DMC-approved dataset will be released along with any DMC decisions regarding publication. The investigators are expected to use only DMC-approved data in future publications. The investigators should submit a copy of the manuscript to the biostatistician to confirm that the DMC-approved data are used appropriately. Once the biostatistician gives final approval, the manuscript may be submitted to external publishers.

12.0 PATHOLOGY REQUIREMENTS – CORRELATIVE STUDIES

12.1 Pharmacokinetics (PKs)

12.1.1 Timing

After determination of the MTD, the last cohort of the phase I portion will be expanded to include an additional 6 patients who will undergo PK testing to evaluate the effect of pazopanib on the pharmacokinetics of temozolomide. The MTD has now been identified at dose level -2 (75 mg/m² per day p.o. days 1-7 and 15-21 of Temozolomide and 400 mg per day p.o. days 1-28 of Pazopanib). As of 12.15.15, all patients moving forward will be treated at this dose. As stated above, the PKs are mandatory for this cohort.

The schedule and dosing for these 6 patients will be as follows:

12.1.1.1 Day 1, Cycle 1

Patients will not take either study drug prior to arriving to the clinic. Patients will have a time = 0 sample drawn, and then be instructed to take their dose of temozolomide. Patients will then have PK samples drawn at 10 min (+/-5 min), 30 min (+/-5 min), 1 hour (+/-5 min), 2 hours (+/-5 min), 3 hours (+/-5 min), 4 hours (+/-30 min), 6 hours (+/-30 min), 8 hours (+/-30 min), and

24 hours(+/- 1 hour) post-dose (drawn on Day 2. This will be the same sample as the pre-dose PK sample of Day 2 provided Day 2 drug administration is done within 1 hour of sample collection. One 3 ml sample is needed).

Pazopanib will be held on this day.

12.1.1.2 Cycle 1, Day 2:

Patients will continue to take temozolomide as instructed but will not take pazopanib until instructed to do so in clinic. Patients will have a time = 0 sample drawn and then be instructed to take their dose of pazopanib. This will be the same sample as the 24-hour post-dose PK sample of Day 1, provided Day 2 drug administration is done within 1 hour of sample collection. If this drug administration is delayed beyond one hour, then another 3 ml PK sample has to be collected for the pre-dose PK of Day 2).

Patients will then have PK samples drawn at 10 min(+/- 5 min), 30 min(+/- 5 min), 1 hour(+/- 5 min), 2 hours(+/- 5 min), 3 hours(+/- 5 min), 4 hours(+/- 30 min), 6 hours(+/- 30 min), 8 hours(+/- 30 min), and 24 hours(+/-1 hour) (done on Day 3) post-dose.

12.1.1.3 Cycle 1, Day 3:

Patients will not take either study drug prior to arriving to the clinic. Patients will have 1 PK sample drawn (the 24 hours[+/- 1 hour] post-pazopanib dose sample from Day 2) and then continue to take both temozolomide and pazopanib as instructed per protocol.

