6.1.2.2 Describe the pharmacokinetics (PK) of the combination of temozolomide and pazopanib

Once the MTD is reached in the phase I portion of the study, this cohort will be expanded to include an 6 additional patients who will have PK studies performed. We will examine the effect of pazopanib on the pharmacokinetics of temozolomide. Full PK profiles will be taken after a single dose of temozolomide on Day 1 and again on Day 2 after administration of the combination of temozolomide and pazopanib. On Day 1, Cycle 1, the patient will have a time = 0 sample, take their dose of temozolomide, and then have samples drawn at the following times:

6.1.2.2.1 Day 1, Cycle 1

Time = 0 (prior to temozolomide dose) 10 min (+/- 5 minutes), 30 min (+/- 5 min), 1 hour (+/- 5 min), 2 hours(+/- 5 min), 3 hours(+/- 5 min), 4 hours (+/- 30 min) , 6 hours(+/- 30 min), 8 hours(+/- 30 min), and 24 hours(+/- 1 hour) post-dose.(drawn on Day 2.This will be the same sample as the pre-dose PK sample of Day 2 provided Day 2 drug administration is done within 1 hour of sample collection. One 3 ml sample is needed).

6.1.2.2.2 Day 2, Cycle 1

Time = 0 (prior to both pazopanib and temozolomide). This will be the same sample as the 24 hour post-dose PK sample of Day 1, provided Day 2 drug administration is done within 1 hour of sample collection. If this drug administration is delayed beyond one hour, then another 3 ml PK sample has to be collected for the pre-dose PK of Day 2), 10 min(+/- 5 minutes), 30 min(+/- 5 min), 1 hour(+/- 5 min), 2 hours(+/- 5 min), 3 hours(+/- 5 min), 4 hours(+/- 30 min), 6 hours(+/- 30 min), 8 hours(+/- 30 min), and 24 hours(+/- 1 hour) (done on Day 3) post dose.

Plasma temozolamide concentrations will be measured using our triple quadrupole API3000 LC-MS/MS after sample preparation by solid-phase extraction. The plasma temozolamide concentration versus time relationships will be modeled using the SAAM II software system (SAAM Institute, Seattle, WA) implemented on a Windows™-based PC as described by Argiris et al. Cmax and Tmax will be taken as the observed values.

These 6 patients in the PK cohort will be included in the phase II analysis. These patients will have correlative studies including MGMT. These 6 patients will be evaluated for phase II endpoints.

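### Section 12.1.1.2 holds only pazopanib before the Day 2 time-0 PK sample, against Section 6.1.2.2.2; read literally, it allows an early temozolomide dose that spoils the shared Day 1 24-hour tube and starts Day 2 sampling late

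*Combined protocol and SAP*

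**What the plan says.** Section 6.1.2.2 sets the aim as the effect of pazopanib on temozolomide PK and describes an assay for plasma temozolomide only. The first profile follows temozolomide alone on Day 1. The second is taken "again on Day 2 after administration of the combination of temozolomide and pazopanib". Section 6.1.2.2.2 defines Day 2 as "Time = 0 (prior to both pazopanib and temozolomide").

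Section 12.1.1.2 gives the operating instruction for the same day: "Patients will continue to take temozolomide as instructed but will not take pazopanib until instructed to do so in clinic". It continues: "Patients will have a time = 0 sample drawn and then be instructed to take their dose of pazopanib". Of that tube it says: "This will be the same sample as the 24-hour post-dose PK sample of Day 1", on condition that Day 2 dosing follows within 1 hour.

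For Day 1 (12.1.1.1) and Day 3 (12.1.1.3) the section states: "Patients will not take either study drug prior to arriving to the clinic". Day 2 has no such sentence. Section 12.1.1.3 then labels the last Day 2 sample, drawn on Day 3, as the 24-hour "post-pazopanib dose sample from Day 2".

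On analysis, Section 6.1.2.2 says: "Cmax and Tmax will be taken as the observed values". Section 9.1.2 also lists Cmin, half-life, clearance, volume and AUCinf, compares each between Day 1 and Day 2 by a Wilcoxon signed rank test, and calls the phase I secondary analyses descriptive.

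**The concern.** Temozolomide is the drug measured, so the Day 2 clock has to start at the temozolomide dose. Section 12.1.1.2 ties the clinic dose to pazopanib, and 12.1.1.3 repeats that anchor, so this is not one stray word. Nothing in 12.1.1.2 tells the patient to leave the Day 2 temozolomide dose until after the draw.

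If temozolomide is taken at home h hours before the draw, two things follow:
- The shared tube contains Day 2 drug. It is then neither a Day 1 24-hour value nor a Day 2 pre-dose value, and no correction of times can undo that.
- Every Day 2 sample is h hours later after the dose than its label. Because Cmax and Tmax are observed values, a peak that passes before the first draw is not seen.

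The 6 patients are the only source for this objective, so one spoiled pair is one sixth of the data.

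**Working it through.** **1. Text comparison.** The plan states no figure to reproduce here.

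| Point | 6.1.2.2.2 | 12.1.1.2 and 12.1.1.3 |
|---|---|---|
| Held until after time 0 | both drugs | pazopanib only |
| Dose named after the draw | the combination | pazopanib only |
| Anchor of the 24-hour draw on Day 3 | after the dose | after pazopanib |

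Table 10 footnote 13 sends sites to both 6.1.2.2 and 12.1 and ranks neither. The notes in 5.2.1 and 5.2.2 send PK-cohort dosing questions to a PK-cohort parameters table. In the text available, Section 7.0 has only Table 10, which gives no Day 2 dose order.

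**2. Illustration of size. All PK inputs are assumed; none is in the documents.** One-compartment oral model with identical true PK on both days:

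C(t) = ka/(ka − ke) × [exp(−ke·t) − exp(−ka·t)], with ke = ln 2 / half-life.

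Half-lives are 1.5, 2, 3 and 4 h; ka is 1.5, 3 and 6 per h; the lead h is 0.5, 1 or 2 h. That makes 12 parameter sets per lead. Sampling times are the protocol's: 0, 10 min, 0.5, 1, 2, 3, 4, 6, 8 and 24 h.

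*One case in full: half-life 2 h, ka = 3, h = 1 h.*
- ke = 0.693/2 = 0.347 and ka/(ka − ke) = 3/2.653 = 1.131.
- Highest Day 1 sample, at 1 h: 1.131 × (0.707 − 0.050) = 0.743.
- Correct 24-hour value: 1.131 × exp(−8.32) = 0.0003, about 0.04% of Cmax.
- With a home dose 1 h earlier, the tube reads C(1) = 0.743, or 100% of Cmax.
- True peak time: ln(3/0.347)/2.653 = 0.81 h. This is less than 1 h, so the peak precedes the first draw.

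*All 36 scenarios*

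| | h = 0.5 | h = 1 | h = 2 |
|---|---|---|---|
| True peak before first draw | 1/12 | 7/12 | 12/12 |
| Observed Day 2 Cmax / correctly sampled Cmax | 1.00-1.04 | 0.84-1.04 | 0.53-1.00 |
| Day 2 AUC0-24 on nominal times / correct | 0.86-0.97 | 0.69-0.92 | 0.43-0.79 |

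The Cmax row counts the shared tube as the first Day 2 sample. Across all scenarios that tube reads 53-102% of Cmax, against 0.002-2.4% with correct dosing.

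**3. What can be recovered.** Dose times are recorded in the drug diary (5.2) and on the sample log (12.1.3).
- Day 1 without the tube: linear trapezoid to 8 h plus C(8)/slope, with the slope from 4, 6 and 8 h. Half-life is 1.000-1.009 of truth and AUCinf 0.997-1.005.
- Day 2, model fit on actual times: least squares on log concentration, samples to 8 h, assumed 10% error, 40 replicates per parameter set. Median AUC is 0.99-1.00 of truth. The 5-95% ranges are 0.93-1.07, 0.93-1.09 and 0.83-1.15 for h = 0.5, 1 and 2, against 0.93-1.08 with correct dosing.
- Day 2, linear trapezoid on actual times: Day 2/Day 1 AUCinf is 0.96-1.00, 0.85-0.99 and 0.63-0.93. A fit is therefore preferable for such patients.

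**4. Should a suspect Day 2 Cmax be discarded?** A rule that sets Cmax aside whenever the first Day 2 sample is the highest would drop 3/12 scenarios at h = 0.5, all with a ratio of 1.00. At h = 1 it would drop 8/12, of which 5 are within about 3% of correct (four at 1.00, one at 0.97). It removes mostly good values at short leads.

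**The case against.** The best defence is that the protocol already gives the right order. Section 6.1.2.2.2 is explicit, and footnote 13 points to it. Section 12.1.1 itself calls the shared tube a pre-dose sample and expects Day 2 dosing within an hour after it. The phrase about continuing temozolomide as instructed can mean as instructed in clinic. Drawing first and then giving both drugs satisfies both sections; home dosing breaches one of them. The amendment log (Amendment 6) records that the laboratory manual was updated with the tube-sharing rule, and the manual may settle the order. A 2-hour lead is also extreme, since 5.2.1 and 5.2.2 recommend taking the two drugs at about the same time.

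Most of that stands. It makes the intended order fairly clear and the harmful reading the less likely one. It does not remove the conflict. Footnote 13 refers to both sections equally, Section 11.7 requires conduct exactly as the protocol describes, and Day 2 lacks the hold that Days 1 and 3 state.

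A reader might go further and infer that patients did take temozolomide at home, or that the Day 1 against Day 2 comparison will show a false fall in exposure. With n = 6, a shift in the same direction in all patients would give the smallest two-sided signed-rank p, 2/64 = 0.031. The documents do not support that inference. They contain no dosing records, they do not say that nominal times will be used, and recorded dose times allow an early dose to be identified.

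**Conclusion.** The conflict is real and should be corrected. Section 12.1.1.2 holds and names only pazopanib, 12.1.1.3 anchors the last Day 2 sample to pazopanib, and 6.1.2.2.2 puts time 0 before both drugs. Literal compliance with 12.1.1.2 could spoil the shared tube and delay the Day 2 profile.

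The reach is narrow. The number of patients affected is unknown and may be zero. Only a descriptive phase I secondary objective in 6 patients is exposed; the MTD, the ORR and the Simon rule are not. In an affected patient, the Day 1 24-hour value (and so the trough), the Day 2 pre-dose value and any missed early Day 2 samples are lost, while half-life and AUC are largely recoverable. The size figures rest wholly on the assumed model, half-lives, absorption rates and leads. The counts out of 12 are points on a chosen grid, not probabilities.

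**What to change.** **Wording**
- In 12.1.1.2, state that on Day 2 patients take neither study drug before arriving, and that temozolomide and pazopanib are taken together in clinic after the time-0 sample.
- State that all Day 2 times, including the Day 3 draw, and the 1-hour tube-sharing rule count from the temozolomide dose.
- Change the pazopanib anchor in 12.1.1.3 to match.
- Point the notes in 5.2.1 and 5.2.2 to 12.1.1.

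**Samples already drawn**
- Analyse by actual time since the recorded temozolomide dose.
- Where that dose preceded the shared tube, do not use the tube as the Day 1 24-hour or Day 2 pre-dose value. Take Day 1 half-life and AUCinf from samples up to 8 hours.
- Report Day 2 Cmax and Tmax as observed, flag these patients, and show results with and without them. Do not declare Cmax and Tmax not evaluable because the first sample is the highest.

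The cost is a few sentences and a short data-handling rule. Dose times are already recorded, so no new forms or samples are needed.

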12.1.2 Sample collection

PK samples will be drawn in the outpatient setting. Collect each blood sample (3 mL) in an evacuated blood tube containing lithium heparin. Invert the tube gently 4 or 5 times (avoid shaking). Care must be taken to ensure that blood does not come in further contact with the stopper on the evacuated tube. Blood samples should be kept in an ice water bath from the time of collection to the time of centrifugation, which should occur within 30 minutes of sample collection. Samples at Northwestern University should be picked up by the Pathology Core Facility Clinical Trials Technician for processing and storage until they are ready to be analyzed. Samples should be labeled with the patient's study ID number and initials, as well as the date and collection time point (i.e. 30 min post-dose).

12.1.3 Processing

Centrifuge samples in a laboratory centrifuge designed for separating plasma from cells at approximately 3,000 rpm for 10 min at 4°C. Transfer the plasma to 2 polypropylene tubes (a primary and a back-up

tube, approximately 0.75 mL per tube). After aliquoting, 30 μ L 8.5% phosphoric acid should be added to each mL of plasma being stored in the polypropylene tubes before freezing the samples (22.5 microL/0.75 mL). Computer-printed labels will be generated at each study site for the polypropylene (storage) tubes detailing study ID number, patient study ID, date of collection, time of collection, and protocol therapy time point. If it should be necessary to handwrite the information, only indelible ink should be used. Apply the labels along the length of the tube. Secure the labels by wrapping with clear tape.

Apply the preprinted labels to the polypropylene tubes at room temperature at least 2 hours before refrigerating or freezing. Adequate adhesion cannot be guaranteed if the labels are applied to cold tubes. Blood samples must be kept frozen at approximately -80°C after collection and until delivery/shipment is initiated.

Sample collection details (i.e., patient study ID, date of collection, time of collection, and protocol therapy time point) should be indicated on a log sheet along with the times of last study drug dose(s). A copy of the sheet should be submitted with the samples.

12.1.4 Shipment

Plasma samples for the PK portion of the study will be shipped directly from study sites to Northwestern University for bioanalysis. Samples should be stored as referenced above until shipment. All samples for all patients on study may be batched and shipped upon completion of the enrollment phase to the PK cohort.

One specimen from each pair of a sample should be included in the initial shipment. Samples will be shipped overnight along with a copy of the log sheet via FEDEX on dry ice to Northwestern University at the address provided below. The remaining set of samples will be saved at each study site until receipt of the first set of samples has been confirmed, then shipped to Northwestern University separately (in case of lost shipment or other complication).

Shipment should only be initiated on Mondays, Tuesdays, or Wednesdays to ensure arrival of samples within working hours Tuesdays through Thursday (excluding holiday dates). [name] should be contacted prior to shipment to confirm shipment date and to notify of expected time and date of delivery.

The address and contact for shipments is as follows:

[name].

Northwestern University Feinberg School of Medicine

Department of Anesthesiology

[name]

[name]
[name]
[contact]
[contact]

Please refer to laboratory manual for further details (available as stand-alone document)

12.2 MGMT Analysis

12.2.1 Tissue requirements

From each patient, 5 unstained slides will be obtained. Paraffin-embedded sections of 4 μ m from the most recent biopsy will be used for immunohistochemistry.

